Study Protocol - intramuscular epinephrine as an adjunctive treatment for severe pediatric asthma exacerbation

Background: In the United States, as many as 1.6 million children present to emergency departments (EDs) each year with an acute asthma exacerbation. Despite extensive research and expert opinion panels, optimal management for severe asthma exacerbations has not been definitively established. Indeed, national guidelines recommend that adjunctive therapies should only be 'considered' given that there is limited or no evidence showing benefit of these therapies in these life-threatening situations.

Epinephrine is a non-selective sympathomimetic that has been used safely for decades. When administered subcutaneously (SQ), it produces bronchodilation within 5-10 minutes. In recent years, intramuscular (IM) administration has become the favored route for patients with anaphylaxis based on studies showing higher peak plasma concentrations with the IM route. Despite this evidence, national asthma guidelines continue to recommend the SQ route when epinephrine is used for severe asthma exacerbation as an adjunct to the primary therapy: inhaled β_2 agonists.

Randomized trials have shown that SQ epinephrine is equally effective compared to inhaled β_2 agonists for the treatment of asthma exacerbation in children. Notably, the combination of SQ epinephrine and nebulized β_2 agonists has not been demonstrated to be more effective in children. One major limitation of these studies is that they did not look specifically at severe asthma on its own. As a result, epinephrine in either form (SQ or IM) is very rarely used for asthma exacerbation and is not considered to be standard first-line therapy.

In summary, prior work in this area has two major flaws. First, previous studies have looked at epinephrine administered SQ and not the potentially superior IM route. Second, no study focused specifically on severe asthma. The latter is notable because markedly poor air entry is one of the hallmarks of severe asthma exacerbation. It is biologically plausible that inhaled treatments could be complemented and enhanced in this subgroup by a drug systemically delivered to the β_2 receptor.

Project Aim: To determine if intramuscular epinephrine is an effective adjunct to inhaled bronchodilators (β_2 agonists) for children with severe asthma exacerbation.

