Baseline data: Once screened, consented, and enrolled, the following demographic data will be collected: birthdate, gender, race, time of arrival to the ED, details of any treatment by a referring provider, symptom type and duration (hours), time since last inhaled bronchodilator (minutes), time since systemic corticosteroids (minutes), number and type of inhaled bronchodilator treatments in the preceding 24 hours, all home medications, drug and food allergies, past medical history, number of hospital admissions for asthma over the prior 12 months, and number of ICU admissions over the child's lifetime. Initial temperature, respiratory rate, heart rate, blood pressure, and pulse oximetry will be recorded. Finally, height, PEFR, and CAS will be measured by the respiratory therapist (RT) immediately prior to the study intervention. Additionally, the subject's family will be asked to complete an Asthma Control Tool (ACT). The ACT is a measure of how well the participant's asthma has been controlled over the preceding three months.

Intervention: Subjects will then be randomly assigned (50% chance) to receive a weight based dose of IM epinephrine 1:1000 or no adjunctive medication. The dose will be 0.2 mg for subjects 20-30 kg and 0.3 mg for subjects greater than 30 kg. This will be injected intramuscularly by an ED nurse into the anterior thigh muscles of the subject using a 1 ml syringe and a 23 gauge one inch needle.

In addition to the study intervention, the standardized treatment pathway based on the current asthma guidelines in use at our center will be utilized. This pathway includes nebulized albuterol, ipratropium bromide, and systemic corticosteroids. The duration and dosages of these other interventions will be administered at the discretion of the treating provider.

Randomization: A block randomization scheme will be used to promote balance at the end of the study. Block randomization ensures that after each block of individuals are enrolled in the study (n individuals in total); an equal number of individuals will be assigned to each group (n/2 individuals in each group). We will use random block sizes of 8-12.

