Allocation concealment: The RT will be blinded as to whether the subject receives a dose of IM epinephrine. Once a patient is determined to be eligible for the study, the research team will complete informed consent/assent. A pharmacy generated randomization schedule will be utilized and sealed envelopes with the allocations (treatment or control) will be kept in the charge nurse's office.

At the time of allocation, the charge nurse will instruct all staff to leave the subject's room. The charge nurse will then open the designated envelope and personally prepare and administer IM epinephrine if the subject is allocated to the treatment arm. If the subject is allocated to the control arm, the charge nurse will draw up a syringe with the appropriate amount of saline as if an injection of epinephrine was going to be given to the participant. The charge nurse will take this syringe into the subject's room, but not administer it. Instead, a 'sham' Band-Aid will be placed over the thigh of the subject. They will be instructed not to reveal to the RT, research team, or bedside nurse whether or not an injection was actually given. Participants and families will be similarly instructed. The RT will remain blinded throughout and will be responsible for measuring all PEFRs and CASs.

Having block sizes that are randomly determined, as well as having larger block sizes of 8-12 will help minimize a member of the research team or the RT guessing the allocation of the next participant and potentially biasing recruitment or assessment. To further assess blinding, at the conclusion of the study, we will ask the RTs to guess which group the subjects they assessed were in.

Study data: The following data will be measured at time points (t_{15} , t_{30} , t_{60} , t_{90} , and t_{120}) minutes following IM epinephrine or sham drug administration: PEFR (if able), CAS, heart rate, respiratory rate, and pulse oximetry. This data will also be recorded at the time of discharge or admission from the ED. Also recorded will be amount and timing of bronchodilator, anticholinergic, and corticosteroid therapy given. Additionally, any other therapies and interventions will be recorded (i.e. oxygen administration, assisted ventilation, magnesium sulfate administration, etc.). ED length of stay as well as disposition will be noted.

Primary outcome measure: Change in percent of predicted PEFR/CAS 15 minutes after the study intervention (t_{15}).

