Recruitment plan: A team of medical student research assistants already in place in the ED will be utilized to help with identifying and consenting potential subjects. Moreover, a research assistant dedicated to the study will be recruiting. All children who present to the ED with an asthma exacerbation while an investigator is available will be screened for eligibility. Based on prior experience, an average of five eligible children will present weekly or 20 per month. If five (25%) of these are recruited monthly, recruitment will be completed in 12 months. If three (15%) are recruited monthly, recruitment will be completed in 20 months.

Risks and benefits:

IM epinephrine has been used for years for the treatment of anaphylaxis in the same doses that will be studied. Severe adverse events are exceedingly rare. These include: cardiac arrhythmia and inadvertent injection into the systemic circulation. The latter could cause a transient, but potentially dangerous increase in the subject's blood pressure. Having the entire study take place in a pediatric emergency department where experts in the management of acutely ill children are immediately available further mitigates this exceedingly small risk. There are transient and minor side effects including anxiety, headache, fear, and palpitations that pass quickly.

At the participant level, the investigators believe there is true clinical equipoise with IM epinephrine in severe asthma exacerbation. However, there is biologic plausibility for a systemic drug to help children whose airways are closed off from severe asthma exacerbation. If the treatment works, subjects who receive epinephrine will breathe better more quickly than if they hadn't received the treatment.

At the societal level, demonstrating the utility of a novel, readily available, inexpensive treatment for severe asthma exacerbation would have far reaching effects for literally hundreds of thousands of children.

Data safety monitoring plan: A knowledgeable physician ([name]) who is not a coinvestigator for this study will serve as the study's safety monitor of adverse events. He will review all clinically significant adverse events within 72 hours. Any clinical adverse events noted by the study personal or the clinical team (MD, RN, RT) will be reported to the monitor within 24

hours. All severe adverse events will be reviewed by the monitor as soon as possible and reported to the IRB within 3 business days.

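### Arrhythmia and the four named side effects are captured only by unsolicited reporting, with no post-injection assessment scheduled before t15 and no by-arm safety analysis except heart rate

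*Combined protocol and SAP*

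**What the plan says.** Risks and benefits names two severe risks, "cardiac arrhythmia and inadvertent injection into the systemic circulation", and then "transient and minor side effects including anxiety, headache, fear, and palpitations that pass quickly". The Data safety monitoring plan lists arrhythmia among the severe adverse events.

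The Study data section sets post-intervention time points at t15, t30, t60, t90 and t120. The items are "PEFR (if able), CAS, heart rate, respiratory rate, and pulse oximetry". The same items are repeated at disposition: "This data will also be recorded at the time of discharge or admission from the ED". Before the intervention, Baseline data provides that "Initial temperature, respiratory rate, heart rate, blood pressure, and pulse oximetry will be recorded".

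Adverse events follow a separate route. Under the Data safety monitoring plan, events that study or clinical staff notice go to the safety monitor within 24 hours, and the monitor reviews clinically significant ones within 72 hours. Severe events go to the IRB within 3 business days.

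The ten Secondary outcome measures include change in heart rate at all five time points, and the Statistical analysis plan gives heart rate its own mixed model. Neither section mentions adverse events.

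Under Allocation concealment, "the charge nurse will instruct all staff to leave the subject's room" at the time of allocation. The charge nurse then injects the drug, or applies a bandage without an injection. The charge nurse and the family are told not to reveal which it was.

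**The concern.** The trial asks whether to add a systemic sympathomimetic to standard care, and the drawbacks it names are mostly brief. A useful answer needs harms counted in the same way in both arms. As written, benefit is measured by a blinded assessor at fixed times, whereas arrhythmia and the four side effects depend on someone noticing and volunteering them.

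Two features make this worse. First, the protocol says that the side effects pass quickly, yet no post-injection assessment is scheduled before t15. Second, those best placed to report early events (the charge nurse, the child and the family) know whether an injection was given, so reporting may differ by arm. Anxiety and fear can also occur in any child with a severe exacerbation. Only identical questions in both arms can show what the intervention adds.

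At stake is whether a report of few or no side effects could be believed, and whether the safety monitor's decisions on these harms would rest on more than volunteered notes.

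**Working it through.** **Step 1: set the named harms against the scheduled items.**

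| Harm named in Risks and benefits | Scheduled post-injection item | By-arm analysis planned |
|---|---|---|
| Cardiac arrhythmia | Heart rate only, no rhythm | Heart rate only |
| Palpitations | Heart rate only, no symptom item | Heart rate only |
| Headache | None | None |
| Anxiety | None | None |
| Fear | None | None |

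**Step 2: timing.** The first scheduled reading is at 15 minutes. For the subcutaneous route, the Background says "it produces bronchodilation within 5-10 minutes". That is a time to bronchodilation, not a time course for harms. It shows that the drug can be acting before t15. With side effects described as passing quickly, some could begin and end before anyone is scheduled to look.

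**Step 3: sample size.** The Power calculation expects 54 analysable participants with up to 10% dropout: 54 / 0.9 = 60, or 30 per arm (27 analysable). This reproduces the stated 60. The documents give no adverse-event rates and no power for harms.

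**Step 4: what zero events would mean with complete recording.** The one-sided 95% upper limit for 0 of n is 1 − 0.05^(1/n).
- n = 30: 9.5%
- n = 27: 10.5%

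For a rare arrhythmia, the chance of at least one event among 30 treated children at an assumed true rate of 1% is 1 − 0.99^30 = 26%. By Fisher's exact test, 5 versus 0 gives p = 0.052 and 6 versus 0 gives p = 0.024. Arrhythmia therefore cannot be usefully compared at this size, however it is recorded.

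**Step 5: the common symptoms under incomplete capture.** Assume true side-effect rates of 40% versus 10%, and let s be the share of events captured, equal in both arms. The observed rates are 0.40s and 0.10s. Exact Fisher power at 30 per arm, two-sided 0.05:

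| s (assumed) | Observed rates | Power |
|---|---|---|
| 1 | 40% vs 10% | 71% |
| 0.75 | 30% vs 7.5% | 49% |
| 0.5 | 20% vs 5% | 24% |
| 0.25 | 10% vs 2.5% | 4% |

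**Step 6: uneven capture.** Suppose a symptom truly occurs in 40% of both arms, and that reporting captures 75% of cases in one arm and 25% in the other (assumed). The expected counts are 30 × 0.40 × 0.75 = 9 and 30 × 0.40 × 0.25 = 3. The apparent ratio is 0.75 / 0.25 = 3 with no true difference. The direction could equally be reversed and hide a real excess.

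**The case against.** The strongest reply is that the plan does have a safety system. The reporting route covers both arms, runs at any time, includes physicians, nurses and respiratory therapists, and has deadlines. Counts by arm could be drawn from it, and heart rate is a scheduled adrenergic measure compared between arms. This stands, and it rules out several stronger readings:

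- **That nothing is recorded before t15.** Baseline vital signs are recorded, and adverse events are reportable at any time. What is missing is a scheduled post-injection assessment before t15.
- **That the harms cannot be compared at all.** They can be counted. The defect is that the counts would be volunteered, probably incomplete, and open to differences in reporting between arms.
- **That the charge nurse is silenced.** The instruction concerns whether an injection was given, and it covers the respiratory therapist, the research team and the bedside nurse. It does not bar reporting an event to the monitor. Nor does the absence of a recording form from these documents prove much, since they contain no case report forms.
- **That staff are absent for 15 minutes.** They leave at allocation; the text does not say when they return.
- **That zero events would be compatible with a true rate of 19% or 38%.** Those values are 9.5% divided by capture shares of 0.5 and 0.25, which the documents do not supply. Even with perfect recording, 30 children leave 9.5%.
- **That intramuscular dosing acts faster than subcutaneous.** The Background claims higher peak concentrations, not faster onset.

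It is also fair to say that symptom questions could threaten blinding, and that anxiety and fear mix the effect of a needle with that of the drug, because controls get no injection. Both points limit the remedy; neither removes the need for it.

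What the reply does not supply is ascertainment. A route for passing on events already noticed sets no question, no time window and no denominator.

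**Conclusion.** The point holds as a weakness of design, not as a contradiction in the documents. Arrhythmia and the four named side effects rely on unsolicited reporting, no post-injection assessment is scheduled before t15, and no by-arm safety analysis is planned apart from heart rate. Any comparison of these harms would be incomplete and vulnerable to uneven reporting.

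The practical gain from scheduled recording lies with the common symptoms. On the assumed 40% versus 10%, full instead of half capture raises power from 24% to 71%. These rates and capture shares are illustrations only. For arrhythmia, scheduled recording would make the count more trustworthy but would not make the arms comparable at 30 each. The change should be made before recruitment, because transient events not recorded at the time cannot be reliably recovered.

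**What to change.** **Study data.** For both arms, add a short yes/no checklist at t15 and t30, each covering the interval since the previous assessment, so that t15 covers 0 to 15 minutes. Items: palpitations, headache, anxiety, fear, and any rhythm abnormality noted (from the bedside monitor if one is in use). Existing staff other than the respiratory therapist ask the questions, after PEFR and CAS have been scored, and the answers stay off the therapist's form.

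**Allocation concealment and Data safety monitoring plan.** The charge nurse reports any event at the injection or sham visit to the safety monitor. These events are then passed to the statistician under coded arm labels, so that they enter the analysis without breaking the statistician's blinding.

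**Secondary outcome measures and Statistical analysis plan.** Add a secondary safety outcome: counts by arm with exact confidence intervals, and Fisher's exact test for the common symptoms. State two limits: 30 per arm cannot compare rare arrhythmias, and differences in anxiety and fear reflect injection plus drug.

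**Cost.** A few tick-box items and one table, with no new staff. Symptom answers may hint at allocation to the person who asks, which could be the bedside nurse; keeping them from the respiratory therapist protects the PEFR and CAS scoring.

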Hypothesis: IM epinephrine is an efficacious adjunct to inhaled bronchodilators (β_2 agonists) for children with severe asthma exacerbation.

Methods:

Study design: This is a repeated measures, parallel group, single-blinded randomized controlled therapeutic trial.

Study site: Kosair Children's Hospital emergency department

Eligible participants: The study population will be comprised of children age 6-17 years old who present to the ED with severe status asthmaticus as diagnosed by the treating provider and verified by peak expiratory flow rate (PEFR) of <60% of predicted prior to intervention or a clinical asthma score of 7 or greater.

Inclusion criteria

- 1. Age greater than 6 years and less than 18 years
- 2. Pre-existing diagnosis of asthma
- 3. Presenting to the ED with an asthma exacerbation

Exclusion criteria

- 1. History of chronic lung or upper airway disease other than asthma
- 2. History significant, uncorrected congenital heart disease or cardiac arrhythmia
- 3. History of thyroid disease, stroke, sickle cell disease, or renal disease
- 4. Systolic blood pressure greater than the 95th percentile for height, age, and gender
- 5. Impending respiratory failure
- 6. Allergy to epinephrine
- 7. Pregnancy
- 8. Weight < 20 kg

Screening procedures: Patients presenting to the ED for asthma exacerbation who meet the inclusion criteria will be considered for enrollment in the study. A brief form will be completed by a study investigator or research assistant to assess for eligibility.

To accurately ascertain predicted PEFR, height will be measured. PEFR testing will be performed by respiratory therapists (RT) in the ED once the patient is brought into a treatment room. The RT will also measure the clinical asthma score.

Girls who meet all of the other screening criteria will be asked if they have achieved menarche. If so, they will be asked to give a urine sample so that a pregnancy test can be performed.

Consent procedures: The study will be described in detail initially. If the parents and patient would like to participate, then a research member will discuss the informed consent and assent (if applicable) with the families and obtain signatures.

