Secondary outcome measures:

1. Change in percent of predicted PEFR/CAS at t₁₅

- 2. Disposition
- 3. Change in percent of predicted PEFR/CAS at t₃₀, t₆₀, t₉₀ and t₁₂₀
- 4. Change in percent of predicted PEFR/CAS at t₃₀, t₆₀, t₉₀ and t₁₂₀
- 5. Change in respiratory rate at t_{15} , t_{30} , t_{60} , t_{90} and t_{120}
- 6. Change in heart rate at t_{15} , t_{30} , t_{60} , t_{90} and t_{120}
- 7. Need for supplemental oxygen at t_{60} , t_{90} and t_{120} (defined as a room air pulse oximetry of <93%)
- 8. Need for albuterol at t_{60} , t_{90} and t_{120}
- 9. Number of hours of albuterol therapy
- 10. ED length of stay

Statistical analysis plan: First straightforward tests for differences among the two groups of individuals will be performed. Analysis of Variance (ANOVA) techniques will be used to test for differences among continuous variables, while Kruskal-Wallis, Fischer's Exact Tests and Wilcoxon methods will be used to test for differences among categorical variables. To examine the outcomes of: (1) change in percent of predicted PEFR/CAS, (2) respiratory rate, (3) heart rate, (4) hours of albuterol therapy and (5) length of stay in the ED, separate mixed-effects general linear models will be developed for each outcome (five models will be developed). The two arms (IM epinephrine and no epinephrine) will be analyzed as fixed effects, and time (time since randomization) will be analyzed as a repeated measures effect. Traditional risk factors (e.g. age, gender, and ethnicity) will be incorporated as covariates during secondary analyses. All main effects and all two-way interaction effects will be investigated for significance from the mixed-effects models developed. Negative binomial regression and logistic regression techniques will also be used to evaluate (7) need for supplemental oxygen and (8) need for albuterol. Life table analysis and Kaplan-Meier techniques will initially be used to analyze the time-related variables (e.g., time to discharge). The Log-rank test will be used to test for differences among survival curves. In addition, Cox (proportional hazards) regression techniques will be developed to test for differences among groups as well as allow for adjustment for additional covariates and risk factors. Cox regression will allow us to investigate all potential main effects and interaction effects. All statistical analyses will be performed by a statistician who is blinded to the treatment allocation of the two groups.

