Planned interim analysis: Interim analyses, reported to the data monitor will be performed at 6, 9 and 12 months after the first participant is randomized. A Lan-DeMets spending function approach will be used to monitor the need for early trial termination.

Power calculation: We will develop separate mixed-effects general linear models for each of the outcomes. For a sample size (n=54) the study has 81% power to detect a 12% main effect of each treatment for each outcome. The estimated power for detecting a 5% interaction effect is 32%. The total sample size required to achieve 80% power to detect an interaction effect, based on the full-factorial designed proposed, is n=1728; which is not a feasible number in which to recruit and enroll. In addition, we will develop Cox proportional hazards regression models to assess the association between group assignment and time related outcomes. For the anticipated sample size (n=54), this study has 80% power to detect a hazards ratio of 1.82 with two-sided α =0.05. Lastly, multiple logistic regression techniques will be utilized to assess

the association between group assignment and dichotomized outcomes. Using the dichotomized version of some outcomes, this study has 80% power to detect on odds ratio of 1.58 with a two sided α =0.05 (n=54). Therefore, we have more than sufficient numbers of participants in each comparison group.

We anticipate that less than 10% of all potential participants will drop out. Therefore, we will recruit a total of 60 individuals for the current study (n=30 per group). This is a feasible sample size for the research team to recruit and enroll in the current study. Power calculations were based on the anticipated total sample size (n=54) that will be available for complete analysis. Using a block randomization scheme (with random block sizes of 8-12), we anticipate that n=30 participants will be assigned to each group.

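### The primary outcome, change in PEFR/CAS at 15 minutes, does not say which measure or which test decides the trial

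*Combined protocol and SAP*

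**What the plan says.** - **Primary outcome measure:** "Change in percent of predicted PEFR/CAS 15 minutes after the study intervention". This is the only definition, and the slash is not explained.
- **Eligible participants:** severity is "verified by peak expiratory flow rate (PEFR) of <60% of predicted prior to intervention or a clinical asthma score of 7 or greater". Under Screening procedures, height is measured so that predicted PEFR can be worked out. A predicted value is therefore tied only to PEFR.
- **Baseline data and Study data:** PEFR and CAS are both planned immediately before the intervention, with no qualification. After it, the list is "PEFR (if able), CAS, heart rate, respiratory rate, and pulse oximetry".
- **Secondary outcome measures:** items 1, 3 and 4 all begin "Change in percent of predicted PEFR/CAS at". Item 1 has the same measure and time as the primary outcome, and items 3 and 4 are identical.
- **Statistical analysis plan:** group comparisons by ANOVA come first for continuous variables. Then "separate mixed-effects general linear models will be developed for each outcome (five models will be developed"), with PEFR/CAS as the first of the five. Arm is a fixed effect and time a repeated-measures effect; every main effect and two-way interaction is to be tested. On blinding, the section closes with "All statistical analyses will be performed by a statistician who is blinded to the treatment allocation of the two groups", which is the only safeguard it names.
- **Planned interim analysis:** three looks are set by calendar time and go to the data monitor. For stopping, the section says "A Lan-DeMets spending function approach will be used to monitor the need for early trial termination", without naming the statistic to be monitored.
- **Power calculation:** a model is promised for each outcome, with 81% power at n=54 for a 12% main effect, said to hold for every outcome.

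**The concern.** A primary outcome should lead any two statisticians to the same test. Here two competent readers could reach different verdicts from the same data. One could test PEFR, the other CAS; one could use ANOVA at t15, the other a main effect averaged over time or an arm-by-time interaction. The test that decides the trial, its error rate, its power and the statistic on which the trial might stop early all depend on a reading that the plan does not supply.

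**Working it through.** **1. Direction of the scales.** Severe disease is PEFR below 60% of predicted, or CAS of 7 or more. Improvement therefore raises PEFR and lowers CAS. The CAS range is not given, but its direction follows from the eligibility cut-off.

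**2. Number of models.** The outcomes listed for mixed models are PEFR/CAS, respiratory rate, heart rate, hours of albuterol and length of stay: five outcomes and five models. Read literally, PEFR/CAS has one model. If a share *w* of children in each arm contributed a raw CAS change and the rest a PEFR change, with benefits of size *p* on PEFR and *c* on CAS, the arm difference would be (1 − *w*)*p* − *wc*. The two benefits would partly cancel. If PEFR and CAS are modelled separately, the count is six, not five.

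**3. Candidate deciding tests.** Two measures, each with an ANOVA comparison, an overall arm effect and an arm-by-time interaction, give 2 × 3 = 6 candidates. None is designated, and the arm difference at t15 from the mixed model is not named at all.

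**4. The plan's own power figure.** The recruitment figure reproduces: 54 / (1 − 0.10) = 60. The 81% cannot be checked, because no SD, alpha or within-child correlation is given for it. The most that can be done is to solve backwards, under these assumptions: 12 percentage points of predicted PEFR, one time point, 27 per arm, alpha 0.05, normal approximation.

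- Two-sided: SD = 12 / [(1.960 + 0.878) × √(2/27)] = 12 / (2.838 × 0.2722) = 15.5 points.
- One-sided: SD = 12 / [(1.645 + 0.878) × 0.2722] = 17.5 points.

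On the two-sided assumptions, power for 12 points would be 95.7% at SD 12, 83.6% at SD 15, 68.8% at SD 18 and 59.7% at SD 20. The stated 81% is for a main effect in a repeated-measures model, so none of these is the plan's power at t15. On the CAS, 12% has no stated meaning.

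**5. Familywise error if either measure may win.** This is an illustration, since the plan states no such rule. Assumptions: two tests, each two-sided at 0.05, one look, bivariate normal statistics with correlation *r*. Two-sided 0.05 appears in the Power calculation only for the Cox and logistic models.

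Error = 1 − P(|Z₁| < 1.96 and |Z₂| < 1.96)

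| *r* | Familywise error |
|---|---|
| 0 | 1 − 0.95² = 9.75% |
| 0.5 | 9.1% |
| 0.7 | 8.3% |
| 0.9 | 7.0% |

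**The case against.** The best defence is that PEFR and CAS were always meant to be analysed separately. The Power calculation promises a model for each outcome, and the duplicated secondary items may be a slip in which one line was for PEFR and the other for CAS. This has force: a single shared model is the literal reading of the five-model count, not an established intention. It does not settle the matter, because separate analysis still leaves open which measure decides and how alpha is shared.

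The second defence is the safeguards: a statistician blinded to allocation, interim results reported to the data monitor, and a spending function. They lower the risk of choosing the measure by its result, but do not define the outcome. A blinded analyst still sees which measure has the smaller p-value. A spending function controls repeated looks at one statistic, not the choice between two.

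Third, it would be unfair to say that the 12% covers no measure, since it is claimed for every outcome. The defect is narrower: it cannot be interpreted on the CAS.

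A reader might also infer three stronger points that the documents do not support:

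- *That children entered on CAS have no baseline PEFR.* The Baseline data section plans PEFR for every child, without the qualifier used at follow-up. Qualifying on CAS does not show that PEFR was absent.
- *That missing PEFR cuts power at t15 to a particular figure.* No missing share is documented, the planned mixed model can keep children with partial data, and power at t15 is not known to begin with.
- *That the trial's error rate is 9.75%.* That holds only if either measure may win, unadjusted, and the two are uncorrelated.

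**Conclusion.** The point holds and must be fixed. The time point is clear; the measure, the contrast and the test are not. Taken literally, the text puts two scales of opposite direction in one linear model. Taken generously, it leaves two measures with no hierarchy and no alpha rule. The interim boundary inherits the same gap.

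The only size that can be given without an assumed SD is the illustrative familywise error of about 7.0% to 9.75%. It rests on an either-measure rule, unadjusted two-sided 0.05, a single look and a correlation between 0.9 and 0. Any power figure for t15 is an assumption until the sponsor supplies the missing inputs.

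**What to change.** Before the first interim look:

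1. Name one primary measure, with its scale and direction. The choice is the sponsor's.
2. Name the arm difference in change from baseline to t15, from that measure's own mixed model, as the single deciding test at two-sided 0.05. Use the same contrast for the Lan-DeMets boundary.
3. Make the ANOVA comparisons and the overall main-effect and interaction tests supportive.
4. Make the other measure a separate first secondary outcome with its own model (six models, not five). Replace secondary items 1, 3 and 4 with distinct PEFR and CAS items.
5. Restate the effect, SD, alpha and power at n=54 for the t15 contrast on the chosen scale. No larger trial is proposed.

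Possible wording: *The primary outcome is [PEFR, percentage points of predicted, higher is better / CAS, points, lower is better]. The primary test is the difference between arms in change from immediately before the intervention to t15, estimated from the mixed model for that measure, at two-sided 0.05.*

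If PEFR is chosen:

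- Model baseline and follow-up PEFR as repeated measures, so that children with partial data are kept, and state the missing-at-random assumption.
- Report PEFR not obtained by arm and time. A child with no PEFR at any time contributes no data, and the text should say so.
- Add a sensitivity analysis that gives the worst rank at t15 only to children who could perform PEFR at baseline but not at t15. Children already unable at baseline should not be ranked last, because their inability is not an event after randomisation.

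The cost is revised text, one extra model and possibly a less favourable stated power.
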